## Study Protocol

The current study tested the impact of multiple exposures to a brief nicotine corrective messaging intervention and nicotine content of study cigarettes on nicotine beliefs and subsequent use of tobacco and nicotine products in a 28-day lab-based study of 74 adults who smoke cigarettes daily. Data were collected at the University of Pennsylvania Center for Interdisciplinary Research on Nicotine Addiction. A parallel population-based study of exposure to nicotine corrective messaging was conducted in adult smokers and non-smokers followed for 12 weeks (NCT04805515).

The lab-based study was a prospective, randomized factorial trial of nicotine corrective messaging (NCM vs. control) and nicotine content of cigarettes (normal vs. reduced) in current daily adult cigarette smokers (minimum 5 daily cigarettes for the past year, carbon monoxide (CO) at least 5 parts per million at Week 0, and no current use of other tobacco or nicotine containing products) for a 35-day protocol. Recruitment occurred through community and campus bulletin boards, local newspapers, radio and television ads, and previous participants who agreed to be re-contacted for non-cessation or non-treatment studies. At the baseline visit (Week 0), eligible, consenting participants provided a CO sample, complete demographic and smoking history measures, and measures of nicotine beliefs and intentions/use of nicotine and tobacco products (see Study Measures). They also provided breath and urine samples for biomarker assessment and continued to smoke their usual brand cigarettes to assess their baseline cigarette smoking behavior. Participants were instructed to continue smoking their own brand cigarettes and collect used filters as a verified count of daily smoking using re-sealable bags provided, while also recording their smoking in a calendar. Participants returned on Day 7 (Week 1; end of baseline), returned used cigarette filters, and were randomized to one of four groups: 1) Nicotine Corrective Messaging (NCM) + RNC cigarettes, 2) NCM + normal nicotine content (NNC) cigarettes, 3) Control + RNC cigarettes, or 4) Control + NNC cigarettes. Participants receiving normal nicotine content or reduced nicotine content cigarettes were explicitly told which product they have been given (i.e., unblinded).

The Nicotine Corrective Messaging (NCM) intervention condition was based on messages tested in our team's pilot study. It included six original messages and two new messages addressing nicotine in cigarette and e-cigarette products that were adapted from several evidence-based sources to be more accessible to a lay audience. The sources consisted of FDA's 2017 comprehensive plan for tobacco and nicotine regulation, FDA's 2013 modifications to labeling of NRT products for over-the-counter human use, the 2014 U.S. Surgeon General's Report on the Health Consequences of Smoking, reports on carcinogens from the International Agency for Research on Cancer, and the NASEM report on the "Public Health Consequences of E-cigarettes." Participants in the NCM condition were exposed to all eight messages in the same order at each exposure.

Participants in the NCM condition received their first exposure to the study messages on Day 7 in the lab. Eye tracking was assessed during a five-second exposure to each educational message, equating to a minimum 40-second exposure. At the end of the session, all participants left with study-provided cigarettes to last until the next visit. Participants continued to collect used filters and record daily number of study cigarettes, non-study cigarettes, and other nicotine or tobacco products used each day for the duration of the study. At lab visits on Days 14 (Week 2), 21 (Week 3), and 28 (Week 4), daily nicotine/tobacco use calendars and used filters were collected at the start of the visit. At the Week 2 visit, all participants completed the first post-exposure measures of nicotine beliefs and intentions/use of nicotine and tobacco products. In visits at Weeks 2-4, participants smoked their study product with CO collected at the start and each smoking session videotaped to extract smoking

behavior. Participants in the NCM conditions were then be exposed to the nicotine corrective messages in the lab and eye-tracking data collected. At the end of the session, all participants left with study-provided cigarettes to last until the next visit, collect used cigarette filters, and asked to track their nicotine and tobacco use via their calendars. The Week 5 visit (Day 35) began with the collection of daily nicotine/tobacco use calendars and used filters and include the final assessment of nicotine beliefs and intentions/use of nicotine and tobacco products in all participants. Participants also provided breath and urine samples for biomarker assessment. Upon completion of assessments, participants in the control conditions (control + NNC cigarettes, control + RNC cigarettes) were exposed to the nicotine corrective messages and all participants were directed to resources on quitting smoking.

## Study Measures

	Aim 1: Population study	Aim 2: Lab study
Intervention/Exposure		
Nicotine messaging vs. control	Wave 1	Week 1
Normal nicotine vs. RNC cigarette		Week 1
Heatmapping	Waves 1-4	
Perceived message effectiveness	Wave 4	Week 5
Message credibility	Wave 4	Week 5
Eye-tracking		Weeks 1-4
Biomarkers		Weeks 0, 5
Outcomes		
Nicotine beliefs	Waves 1, 2, 4	Weeks 0, 2, 5
Intention to use nicotine/tobacco products	Waves 1, 2, 4	Weeks 0, 2, 5
Nicotine/tobacco use and behavior	Waves 1, 2, 4	Weeks 0, 2, 5
Subjective rating of study cigarette		Weeks 1-5
Manipulation check	Waves 1, 2, 4	Weeks 0, 2, 5
Moderators		
Sociodemographics	Wave 1	Week 0
Literacy	Wave 1	Week 0
Cancer risk beliefs	Wave 1	Week 0
Cancer risk behaviors	Wave 1	Week 0
Fagerstrom test for nicotine dependence	Wave 1	Week 0
Other key constructs		
Attitudes about nicotine	Waves 1, 2, 4	Weeks 0, 2, 5
Nicotine-related norms	Waves 1, 2, 4	Weeks 0, 2, 5
Behavioral control	Waves 1, 2, 4	Weeks 0, 2, 5
Stages of change	Wave 1, 4	Week 0, 5
Policy support	Wave 4	Week 5

## Statistical Analysis Plan

Sample Size. Power for Aim 2 was calculated for 160 adult current daily cigarette smokers using an ANCOVA framework to detect differences between any two study conditions; with n=40 in each of the four conditions in the trial, we will have 80% power to detect medium effect sizes (Cohen's  $f = 0.33$ ) in continuous outcomes (i.e., nicotine beliefs, behavior, subjective ratings), assuming three covariates in the model (i.e., age, gender, cigarettes per day at baseline). In addition, using a two-way analysis of variance framework, 40 participants in each study condition provides 85% power to detect a statistically significant moderation of these same outcomes by the nicotine content of the study cigarettes, assuming that the responses by those in the NCM + NNC condition differ from those in the other three conditions by 1 standard deviation. Sample size for the eye tracking analyses is based on our earlier work that recruited 200 participants to a 2 x 2 factorial design and used the same outcomes (i.e., dwell time, time to first area of interest).

Data Preparation. We will conduct data screening steps similar to Aim 1 including assessing outliers, missing data presence/patterns, and normality/equality of variance assumptions. Non-normal data will be transformed as needed. In all analyses, the assumptions underlying the application of all the statistical methods that are used will be examined, principally using standardized residuals, influence diagnostics, and graphical displays. Where needed, appropriate transformations will be applied to ensure that data meet model assumptions. Descriptive analyses will characterize participants overall and by study condition. Aim 2 eye tracking data will be cleaned and pre-processed using standard procedures from our previous work. Descriptive analyses will characterize participants overall and by study conditions. Bivariate tests will assess for differences in participant characteristics by conditions and examine if any baseline variables that are imbalanced between study groups are associated with primary and secondary outcomes ( $p < .10$ ). Any such variables will be accounted for in analyses as covariates.

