### Analytic Approach.

**Aim 2: Test the impact of NCM (messaging vs. control) and nicotine content of cigarettes (normal vs. reduced) on nicotine beliefs and subsequent use of tobacco and nicotine products using a 2 x 2 factorial design in a sample of 160 adult current smokers followed for 4 weeks.**

*Hypothesis 2a:* Adult smokers in the NCM + normal nicotine content (NNC) cigarette condition will report the fewest false beliefs about nicotine compared to those in the NCM + RNC and control conditions (Control + RNC cigarettes, Control + NNC cigarettes); those in the Control + NNC cigarette condition will report the highest study cigarette use.

*Hypothesis 2b:* Lower subjective ratings of study cigarettes (e.g., strength) will predict greater false beliefs about RNC cigarettes.

Analyses for Aims 1 and 2 employ common measures and a common analytic framework to test the impact of nicotine education on nicotine beliefs and behavior. Primary analyses will use an intention-to-treat approach, employing a general linear mixed model to accommodate missing data. Outcomes for **Aim 2** focus on continuous outcomes (*primary outcome*: nicotine beliefs; *secondary outcomes*: frequency and intensity of nicotine/tobacco use), with the primary hypotheses (**Hypotheses 2a**) focused on the effect of the two interventions (nicotine education and nicotine content of study cigarettes) on these outcomes. Preliminary analyses will examine differences in these outcomes across study conditions at the first post-exposure time point (Week 2) and at the final timepoint (Week 5) using ANCOVA controlling for covariates that are differentially distributed between study groups. These outcomes as well as measures of tobacco use (study cigarette use, topography patterns, CO) will then be analyzed using the general linear model approach to repeated measures analysis. Of primary interest in Aim 2, we will evaluate

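### The SAP's 80% and 85% power are for 160 participants, the protocol reports 74, and nothing reconciles them; at 74 the planned 1-SD interaction has about 56% power before any variance reduction

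*Combined protocol and SAP*

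**What the plan says.** The SAP, under Sample Size, makes two power statements, both for 160 participants.

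- For a difference between any two conditions at Cohen's f = 0.33: "with n=40 in each of the four conditions in the trial, we will have 80% power to detect medium effect sizes". The model is an ANCOVA, "assuming three covariates in the model (i.e., age, gender, cigarettes per day at baseline"; no R-squared is given.
- For the interaction: "40 participants in each study condition provides 85% power to detect a statistically significant moderation of these same outcomes by the nicotine content". The effect behind this figure is a single cell, messaging with normal-nicotine cigarettes, standing 1 SD apart from each of the rest.

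The Aim 2 statement under Analytic Approach repeats the number: "in a sample of 160 adult current smokers followed for 4 weeks". The Study Protocol section, in the past tense, reports the messaging and nicotine-content experiment "in a 28-day lab-based study of 74 adults who smoke cigarettes daily".

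The same Analytic Approach section sets the main model: "Primary analyses will use an intention-to-treat approach, employing a general linear mixed model to accommodate missing data". It introduces the interaction with "Of primary interest in Aim 2, we will evaluate". The moderation steps then test the interaction at p < .05. Step 2 looks at its direction and size only if it is significant; step 3 otherwise enters cigarette condition as a covariate. The steps do not say whether the interaction estimate and its interval are reported when the test is not significant.

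**The concern.** The combined document carries two sample sizes, and its only power figures belong to the larger one. The reported 74 is 46% of the planned 160 (74/160 = 0.4625).

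What is at stake is how a non-significant interaction is read. A reader who takes the 85% at face value expects a true 1-SD moderation to be missed about 15% of the time. At 74 the miss rate is about 44%, 31% or 15% for error-variance reductions of 0, 25% or 50%. The interaction is the result the SAP singles out, and its size is examined only when it is significant. A null test could therefore be given more weight than the sample supports.

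**Working it through.** **Inputs from the documents.** 40 per condition; f = 0.33 for two conditions; a 1-SD difference of one cell from the other three; three covariates; p < .05 for moderation; 74 participants.

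**Assumptions.** Two-sided alpha .05; cells of 18, 18, 19 and 19 (18.5 on average); effects in unadjusted SD units; v = fraction of error variance remaining. The values v = 1, 0.75 and 0.5 are illustrative. All power values come from the noncentral F distribution with 1 numerator df and noncentrality λ.

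**1. The plan's own figures at 160.**
- Two conditions: d = 2f = 0.66, λ = d²/(2/n) = 0.4356/(2/40) = 8.71, df = 2×40 − 5 = 75. Power 83% (stated 80%).
- Interaction: if one cell is 1 SD from the other three, the contrast is 1 SD. λ = 1/Σ(1/nᵢ) = 1/(4/40) = 10, df = 160 − 7 = 153. Power 88% (stated 85%).

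The stated values correspond to about 37.1 and 36.4 per condition, so they are about 3 points conservative at 40.

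**2. The same formulas at 74.** Interaction: Σ(1/nᵢ) = 2/18 + 2/19 = 0.2164, SE = √(0.2164v), df = 67. At v = 1, λ = 1/0.2164 = 4.62 and the 95% CI half-width is 1.996 × 0.465 = 0.93 SD. Two conditions: λ = 0.4356/(2v/18.5), df = 32; at v = 1, λ = 4.03.

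| At 74 | v = 1 | v = 0.75 | v = 0.5 |
|---|---|---|---|
| Interaction, 1 SD | 56% | 69% | 85% |
| Interaction, 0.5 SD | 19% | 23% | 32% |
| Two conditions, f = 0.33 | 49% | 61% | 79% |
| Interaction 95% CI half-width (SD) | 0.93 | 0.80 | 0.66 |

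With 18 or 19 in each cell and v = 1, the two-condition power is 48% or 51% and the interaction power 55% or 58%. At 160 with v = 1 the half-width is 0.62 SD.

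**3. Variance reduction needed at 74.** The interaction reaches 80% at v = 0.57 (a cut of about 43%) and 85% at v = 0.50. The two-condition comparison reaches 80% at v = 0.48 (a cut of about 52%).

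**4. Main effect, 37 against 37.** At f = 0.33, λ = 74 × 0.33² = 8.06, df = 67, v = 1: power about 80%. Under the SAP's one-cell 1-SD pattern each main effect is only 0.5 SD, and its power equals that of the interaction (56% at v = 1).

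**5. What the repeated-measures model might give.** Assume compound symmetry with correlation ρ between visits and the same effect at Weeks 2 and 5. Power for a 1-SD interaction at 74:

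| Analysis | v | ρ = 0.3 | ρ = 0.5 | ρ = 0.7 |
|---|---|---|---|---|
| Mean of Weeks 2 and 5, baseline-adjusted | (1+ρ)/2 − ρ² | 81% | 85% | 94% |
| Mean of Weeks 2 and 5, unadjusted | (1+ρ)/2 | 75% | 69% | 63% |
| Week 5, baseline-adjusted | 1 − ρ² | 60% | 69% | 84% |

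If the model instead tests change from Week 0, v can exceed 1. At ρ = 0.3, Week 5 minus Week 0 has v = 2(1 − 0.3) = 1.4 and power 43%. The mean of Weeks 2 and 5 minus Week 0 has v = 0.65 + 1 − 0.6 = 1.05 and power 54%.

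**The case against.** The best defence is that nothing stated is false. The power was calculated for 160, in the future tense; the 74 describes what was done. Recruiting fewer than planned is not a design error. That stands: a reader might infer that the SAP miscalculated its power or claims 85% for 74 people, and it does neither. What is missing is the link between the two numbers.

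Second, 56% is not the power of the planned primary analysis. It assumes one visit and no variance reduction, whereas the SAP plans a mixed model and beliefs are measured at Weeks 0, 2 and 5. A reader might infer that the interaction is fixed at 56% unless error variance is halved. The documents do not support that: a cut of about 43% already gives 80%, and baseline-adjusted means give 81% to 94% under the assumptions shown. Equally, they do not guarantee recovery. Baseline beliefs are not among the three covariates in the power statement, no correlation is given, and change-from-baseline models can fall below 56%.

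Third, the primary hypotheses also concern the effects of the two interventions, and a 37-against-37 main effect at f = 0.33 keeps about 80%. This is correct and belongs in any restatement. It does not rescue the stated 80%, which is for any two conditions.

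Fourth, finding no evidence of moderation is not claiming its absence, and silence about an interval does not show that it will go unreported. Also correct, so step 3 can stay. Nor should 1 SD become a cut-off for ruling moderation out. It is a power assumption, not a threshold of importance: in simulations with no true interaction, 64% to 71% of intervals that exclude 1 SD still include 0.5 SD (v from 0.5 to 1).

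**Conclusion.** The point holds as an unreconciled sample size and should be fixed. The 80% and 85% are sound, slightly conservative planning figures for 160; they do not describe a study of 74.

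The size of the loss depends on unstated variance assumptions, so it can be given only as scenarios. Variance reductions of up to half span about 56% to 85% for the 1-SD interaction, but these are not bounds: the repeated-measures cases examined run from 43% to 94%. A 0.5-SD interaction stays poorly powered, at 32% even with error variance halved.

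The figures rest on near-equal cells, two-sided alpha .05 and all 74 being evaluable. Fewer evaluable participants would lower power further.

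**What to change.** **Sample Size.** Label 160 (40 per condition) and its 80% and 85% as the original planned target. Add a dated statement that 74 were achieved, saying whether that means enrolled, randomized or analysed. Give the power and interval half-widths at 74 for error-variance reductions of 0, 25% and 50%, with their assumptions, including the 0.5-SD row and the main-effect figure of about 80%. Note that a change-from-baseline model with low correlation between visits could do worse.

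**Aim 2 text.** Show 160 planned and 74 achieved.

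**Moderation steps.** Keep step 3 and its covariate model as written. Add, dated as a post-conduct reporting addition, since the protocol's past tense indicates that the study has been run: *The NCM x cigarette interaction estimate and 95% CI are reported whatever the p-value, and a p-value of .05 or above is not in itself read as absence of moderation.* Attach no decision rule to 1 SD.

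**Cost.** One paragraph, one phrase and one sentence, with no new participants or data. The stated power becomes less favourable and reporting grows slightly.

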### Analytic Approach.

**Aim 2: Test the impact of NCM (messaging vs. control) and nicotine content of cigarettes (normal vs. reduced) on nicotine beliefs and subsequent use of tobacco and nicotine products using a 2 x 2 factorial design in a sample of 160 adult current smokers followed for 4 weeks.**

*Hypothesis 2a:* Adult smokers in the NCM + normal nicotine content (NNC) cigarette condition will report the fewest false beliefs about nicotine compared to those in the NCM + RNC and control conditions (Control + RNC cigarettes, Control + NNC cigarettes); those in the Control + NNC cigarette condition will report the highest study cigarette use.

*Hypothesis 2b:* Lower subjective ratings of study cigarettes (e.g., strength) will predict greater false beliefs about RNC cigarettes.

Analyses for Aims 1 and 2 employ common measures and a common analytic framework to test the impact of nicotine education on nicotine beliefs and behavior. Primary analyses will use an intention-to-treat approach, employing a general linear mixed model to accommodate missing data. Outcomes for **Aim 2** focus on continuous outcomes (*primary outcome*: nicotine beliefs; *secondary outcomes*: frequency and intensity of nicotine/tobacco use), with the primary hypotheses (**Hypotheses 2a**) focused on the effect of the two interventions (nicotine education and nicotine content of study cigarettes) on these outcomes. Preliminary analyses will examine differences in these outcomes across study conditions at the first post-exposure time point (Week 2) and at the final timepoint (Week 5) using ANCOVA controlling for covariates that are differentially distributed between study groups. These outcomes as well as measures of tobacco use (study cigarette use, topography patterns, CO) will then be analyzed using the general linear model approach to repeated measures analysis. Of primary interest in Aim 2, we will evaluate

whether using study cigarettes with a known nicotine content (i.e., normal or reduced) moderates the effect of NCM on our primary and secondary outcomes by incorporating an interaction between NCM condition (NCM/control) and study cigarette condition (NNC/RNC) through the following steps: 1) bivariate analyses, to determine if outcomes vary by these variables; 2) testing whether study cigarette condition moderates ( $p < .05$ ) experimental effects in the models above; if so, performing post-hoc statistical testing to examine the direction and magnitude of the moderation; 3) if no evidence of moderation exists, including study cigarette condition as a covariate.

Our previous work highlights that assessing perceptions of RNC cigarettes that find an association between participants perceiving that their assigned product is low nicotine and reporting lower harm perceptions of the product. To address **Hypothesis 2b**, we will also use autoregressive, cross-lagged panel analysis to examine the direction of the relationships between subjective ratings and nicotine beliefs over three timepoints (Weeks 0, 2, and 5) and whether the regression paths vary in magnitude by study condition.

As in Aim 1, our exploratory analyses will focus on three areas: 1) potential moderators of the relationship between intervention condition and the study outcomes; 2) nicotine beliefs as a potential mediator of the relationship between intervention condition and constructs identified in the Theory of Planned Behavior (i.e., nicotine-related attitudes, norms, behavioral control, and nicotine/tobacco intentions and use); and 3) the relationship between visual attention to nicotine education messages and nicotine beliefs in the participants exposed to the NCM intervention.

For the first area (*moderation*), we will conduct exploratory analyses using the same steps described for Hypothesis 2a to determine whether there are potential moderators of the relationship between the study condition (NCM + RNC, NCM + NNC, Control + RNC, Control + NNC) and outcomes, specifically age, gender, baseline cancer beliefs and cancer risk behaviors.

For the second area (*mediation*), we will draw from traditional mediation frameworks and use robust methods to explore the relationships outlined in our theoretical framework and whether changes in nicotine beliefs post-exposure (Weeks 2, 3, 4) influence nicotine-related attitudes, norms, behavioral control, intention, and behavior at the final assessment (Week 5). To complement Aim 1 analyses, we will examine whether nicotine beliefs at Week 2 are associated with these Week 5 outcomes using bivariate statistics and the general linear model-based analysis accounting for any covariates as described above. Where these preliminary steps indicate potential correlation between nicotine beliefs and study outcomes ( $p < .05$ ), we will test for mediation by estimating the indirect effects of nicotine beliefs on follow-up outcomes via the study condition using a bias-corrected bootstrapping method with 1,000 resamples. This approach estimates indirect (i.e., mediation) effects and produces bias-corrected asymmetric 95% CIs correcting for non-normality of the distribution of indirect effects and providing higher power and better control over the Type I error rate versus traditional approaches to test mediation. Asymmetric 95% confidence intervals around indirect effect estimates for nicotine beliefs that do not include zero will be interpreted to indicate significant mediation.

For the third area (*visual attention*), we will identify the regions of interest (ROIs) in each nicotine education message based on responses to the Aim 1/Wave 1 heatmap task. Using eye-tracking, we will explore whether attention to the ROIs (i.e., dwell time, fixations) is correlated with scores on the nicotine beliefs scales (i.e., nicotine, NRT, e-cigarette, RNC cigarette beliefs) at the same assessment (Weeks 1-4). Given the content of messages in the nicotine education condition, we will be able to assess whether attention to specific ROIs is correlated with specific beliefs (i.e., whether attention to a specific ROI within the “Nicotine does not cause cancer” is correlated with response to the nicotine belief item regarding nicotine causing cancer). We will also be able to explore the prospective relationship between visual attention to the nicotine

education messages (e.g., duration spent viewing messages, attention to ROIs) and nicotine beliefs and whether there are differences in visual attention in the NCM intervention condition over the four weeks of data collection. These data will inform potential refinements to nicotine education messages for future studies.

Missing data: The most effective approach to eliminating biases and inefficiency caused by missing data is to collect complete data. In both aims of our study, we will use several tools available to maintain contact and verify that forms are complete. Use of computerized survey platforms (e.g., Qualtrics) in this study will provide additional mechanisms to improve completeness of survey responses, but even so, some participants may refuse to answer certain questions. We anticipate that one cause of missing data will be item non-response on self-report questionnaires; another will be missing assessments. Finally, missing data can arise through attrition; however, the steps outlined in the proposal are meant to minimize this. The general/generalized linear mixed model that we will be using for analysis for Aim 2 is a maximum likelihood approach to repeated measures analysis of variance that does not rely on imputation, which may give differing results depending upon the exact imputation procedure used. Rather, this approach estimates the parameter values that would maximize the probability of observing the data collected. In the event of missing variables, the likelihood for a given individual is the probability of observing the non-missing variables. Thus, the maximum likelihood approach allows the use of data from subjects for the time period for which data is available, but not for time periods for which the data is missing. This procedure uses information from earlier time periods to estimate the effects of later time periods, while also accounting for the uncertainty of the projection in the computation of standard errors and test statistics. Maximum likelihood estimation is considered superior to imputation methods for the treatment of missing data in clinical trials.

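### The plan does not commit the tobacco-use analysis to the verified Day 0-7 baseline count or to the Week 3 and Week 4 returns, although the trial collects them all

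*Combined protocol and SAP*

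**What the plan says.** **Outcome.** Under Analytic Approach (Aim 2), the secondary outcomes are "frequency and intensity of nicotine/tobacco use". No variable, data source or time window is given for them.

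**Named times.** The Study Measures row reads "Nicotine/tobacco use and behavior Waves 1, 2, 4 Weeks 0, 2, 5", the last part being the lab study. In Analytic Approach, a comparison of the conditions that the plan labels preliminary is made "at the first post-exposure time point (Week 2) and at the final timepoint (Week 5", by ANCOVA that controls for covariates distributed differently between groups.

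**Repeated measures.** The next sentence adds that "measures of tobacco use (study cigarette use, topography patterns, CO) will then be analyzed using the general linear model approach to repeated measures analysis". It names no weeks and no baseline.

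**Covariates.** The Sample Size paragraph assumes age, gender and baseline cigarettes per day as covariates, without saying where the baseline count comes from. Data Preparation admits a baseline variable only if it is imbalanced between groups and associated with an outcome (p < .10).

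**Data collected.** Under Study Protocol, from the Week 0 visit participants "continued to smoke their usual brand cigarettes to assess their baseline cigarette smoking behavior", keeping used filters and a calendar, and returned the filters on Day 7 (Week 1), the day of randomisation. After that, "At lab visits on Days 14 (Week 2), 21 (Week 3), and 28 (Week 4), daily nicotine/tobacco use calendars and used filters were collected", and again on Day 35 (Week 5).

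**The concern.** Weeks 0, 2 and 5 are the times of the belief and intention questionnaires. They do not match the daily use record. Filter collection starts after the Week 0 visit, so no verified count exists at Week 0. Study cigarettes are first handed out on Day 7, so study cigarette use has no Week 0 value either. The week that the protocol sets aside to measure baseline smoking is returned at Week 1, which is not among the named times. The records for Days 14-21 and 21-28, returned at Weeks 3 and 4, are not among them either.

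Two things are at stake. The first is precision: baseline smoking is likely to predict later smoking strongly, yet the written rule would drop it from the model whenever randomisation happened to balance it. The second is analyst discretion. The same records support an analysis of Week 5 only, of Weeks 2 and 5, or of all four weeks, from survey or filter counts, with either baseline. The predicted ordering of study cigarette use in Hypothesis 2a could be tested in any of these ways.

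**Working it through.** **Step 1: match returns to named times.**

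| Return visit | Period covered | Among the named times (0, 2, 5)? |
|---|---|---|
| Week 1 (Day 7) | Days 0-7, own brand | No |
| Week 2 (Day 14) | Days 7-14 | Yes |
| Week 3 (Day 21) | Days 14-21 | No |
| Week 4 (Day 28) | Days 21-28 | No |
| Week 5 (Day 35) | Days 28-35 | Yes |

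Two of five returns coincide with the named times. The baseline return and two of the four treatment weeks do not.

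**Step 2: set up the variance.** The plan has no figure of its own to reproduce here, and its power statements are not used. The correlation r between weeks is my assumption. Weekly counts have variance 1. V is the variance of the mean of the chosen treatment weeks, and c is that mean's covariance with the Day 0-7 count. The variance after adjustment for baseline is V - c².

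- Compound symmetry, k weeks: V = (1 + (k-1)r)/k and c = r.
- AR(1), with the correlation falling by a factor r per week from Week 1:
  - Four weeks: V = (4 + 2(3r + 2r² + r³))/16 and c = (r + r² + r³ + r⁴)/4.
  - Weeks 2 and 5: V = (1 + r³)/2 and c = (r + r⁴)/2.

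**Step 3: gain from always adjusting for the verified week (four-week mean).**

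| | r = 0.6 | r = 0.7 | r = 0.8 |
|---|---|---|---|
| Compound symmetry, V | 0.700 | 0.775 | 0.850 |
| V - c² | 0.340 | 0.285 | 0.210 |
| Ratio | 49% | 37% | 25% |
| AR(1), V | 0.592 | 0.678 | 0.774 |
| V - c² | 0.485 | 0.481 | 0.425 |
| Ratio | 82% | 71% | 55% |

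For example, AR(1) with r = 0.8 has c = (0.8 + 0.64 + 0.512 + 0.4096)/4 = 0.5904, so 0.774 - 0.349 = 0.425.

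This takes own-brand baseline smoking to correlate with study-cigarette weeks as those weeks correlate with each other. If it carries only 85% of that correlation, c becomes 0.85c. The ratios for r = 0.6 and 0.8 are then 63% and 46% under compound symmetry, and 87% and 67% under AR(1).

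**Step 4: gain from adding Weeks 3 and 4 (baseline-adjusted, equal weights).**

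| | r = 0.5 | 0.6 | 0.7 | 0.8 | 0.9 |
|---|---|---|---|---|---|
| Compound symmetry, four weeks | 0.375 | 0.340 | 0.285 | 0.210 | 0.115 |
| Weeks 2 and 5 | 0.500 | 0.440 | 0.360 | 0.260 | 0.140 |
| Ratio | 0.75 | 0.77 | 0.79 | 0.81 | 0.82 |
| AR(1), four weeks | 0.461 | 0.485 | 0.481 | 0.425 | 0.282 |
| Weeks 2 and 5 | 0.483 | 0.475 | 0.451 | 0.390 | 0.259 |
| Ratio | 0.95 | 1.02 | 1.07 | 1.09 | 1.09 |

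Under AR(1) adjacent weeks add little, and an equal-weight mean can be up to 9% worse than Weeks 2 and 5. If the effect is constant over weeks and the model chooses the weights, four weeks are never worse. Under AR(1) the information is (1 + 3(1-r)²)/(1-r²) for four weeks and 1/(1-r²) + (1-r³)/(1+r³) for two. The two-to-four information ratio, which is the four-to-two variance ratio, runs from 0.90 (r = 0.5) to 1.00 (r = 0.9).

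**Step 5: against Week 5 alone.** The adjusted Week 5 variance is 1 - r² under compound symmetry and 1 - r⁸ under AR(1). The equal-weight four-week mean has 46-61% of it across both structures (r 0.5-0.9).

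**The case against.** The quoted time points belong to an analysis that the plan itself calls preliminary. The primary analysis is a mixed model, and the sentence on repeated measures excludes no week. CO is in that sentence and is collected at the Weeks 2-4 smoking sessions, so the model cannot be confined to Weeks 0, 2 and 5. The table row "Nicotine/tobacco use and behavior" runs parallel to the survey waves of Aim 1, and the table has no row for filters, calendars, topography or CO. It may describe only the questionnaire. The baseline cigarettes per day in the power statement could well be the verified week. Weeks 2 and 5 are also meaningful contrasts: after the first exposure and at the end.

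All of this stands, and it rules out two stronger readings that a reader might infer:

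- *That the plan discards the baseline week and half the treatment record.* Leaving the weeks unnamed does not exclude any of them.
- *That baseline is recalled and follow-up counted, so that a change of instrument would appear as change over time.* No text says that the Week 0 self-report is the baseline for counted use. If the row is the survey, Weeks 0, 2 and 5 use one instrument and no such shift arises.

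The objection does not supply the missing commitment. On the survey reading, the filter-verified record has no stated role in the secondary outcomes. On the other reading, no Week 0 count exists. Either way the weeks, source and baseline of the use model remain open.

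**Conclusion.** The point holds as a gap in specification, not as an error of analysis. The only times named for tobacco use pass over the verified baseline return and the Week 3 and Week 4 returns. The model that could use them does not say that it will, and the covariate rule makes baseline adjustment depend on chance imbalance.

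The firmer gain is from always adjusting for the Day 0-7 count. It appears under both correlation structures, and its size rests on the assumed r and on baseline smoking predicting study-period smoking. The gain from Weeks 3 and 4 is not firm: worthwhile under compound symmetry, little or none under AR(1). It would be wrong to say that precision is certainly lost by using Weeks 2 and 5. The point concerns study cigarette use and the secondary outcomes and leaves the primary belief outcome untouched. It is a minor, inexpensive improvement.

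**What to change.** In Analytic Approach, for cigarettes per day and study cigarette use:

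1. Define the outcome as the four weekly calendar/filter counts over Days 7-14, 14-21, 21-28 and 28-35, and fit the mixed model to these.
2. Always include the Day 0-7 calendar/filter count as a baseline covariate, whether or not it is imbalanced between conditions.
3. Keep a week-by-condition term, so that the Week 2 and Week 5 contrasts are still reported beside the four-week average.
4. Keep Weeks 0, 2 and 5 for beliefs, intentions and the survey use items, and say that the Study Measures row refers to those items if that is what is meant.

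The cost is SAP wording and data derivation, since the calendars and filters are already collected for every week. There is one small downside: a four-week average mixes periods after one to four message exposures, which is why the week-by-condition term is needed. With that term in the model, the four-week average is in effect the equal-weight one, so the possible loss of up to 9% under AR(1) applies to it. The Week 2 and Week 5 contrasts remain available.
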